#### 10.4 ADVERSE EVENT REPORTING

Complications due to hypothermia include bradycardia or arrhythmias, a reduced immune system, blood clotting, increased insulin resistance, and electrolytes to shift, causing potassium levels to appear low because of increased absorption into cells(33;49). However, patients treated with intravascular cooling do not experience the complications of skin rashes, burns and skin death(33). Intravascular cooling catheters function as central venous catheters and contain working ports that facilitate routine critical care such as administering drugs and fluids and drawing blood.

Safety assessments will consist of monitoring and reporting adverse events (AEs), selected adverse events of interest, and serious adverse events (SAEs), both anticipated and unanticipated. An Adverse Event is any undesirable and unintended, although not necessarily unexpected, event occurring in human subjects as a result of (a) the interventions and interactions used in the research; or (b) the collection of identifiable private information under the research. A Serious adverse event is an adverse event that led to death, or to serious deterioration in the health of the subject, that resulted in death, was life-threatening, required hospitalization (initial or prolonged), resulted in disability or permanent damage, congenital anomaly/birth defect, required intervention to prevent permanent impairment or damage, or other serious events (Important Medical Events). NOTE: Planned hospitalization for a preexisting condition, or a procedure required, without serious deterioration in health, is not considered a serious adverse event. An unanticipated adverse device effect as defined by FDA regulations, 2CFR 812.3(s) is any serious adverse effect on health or safety or any life- threatening problem or death caused by, or associated with, a device, if that effect, problem, or death was not previously identified in nature, severity, or degree of incidence in the investigational plan or application (including a supplementary plan or application), or any other unanticipated serious problem associated with a device that relates to the rights, safety, or welfare of subjects.

Each clinical site is instructed to report all fatal events, SAEs, and other unanticipated problems in the central database within 24 hours of first knowledge of the event. Additionally, all current study data for that particular subject must be entered to allow for timely review by the internal and external medical monitors. Upon entry of a SAE, the central database triggers notification of the SAE to the medical monitor. Following formal review, the SAE is forwarded to the DSMB for review.

The independent Research Monitor for the HOPES Trial is [name], Chairman of the DSMB. [name] has applicable expertise in managing neuro-critical care patients, the use of temperature management and treatment with hypothermia; he is a former member of his local IRB and is an experienced, highly regarded researcher. He is an expert with the nature of risk(s) identified in the research protocol, and he is independent of the team conducting the research involving human subjects. He has no conflict of interest and is not be under the supervision of the PI, other investigators or research staff. [name], as the independent research monitor, will identify to the research team any concerns regarding safety, ethical and scientific integrity. Serious, unexpected, related events are reported to the IRB by the site PI. [name] comments on these events will be included in the IRB reporting. [name] as the independent Research Monitor has the authority to stop the research protocol in progress, remove individual human subjects from a research protocol, and take whatever steps are necessary to protect the safety and well-being of human subjects. The research monitor will review adverse events reported to him by the study team and, report if he agrees with the site- Pl's assessment of relationship to the study. The research monitor reviews the principal investigators reports on serious adverse eents and indicats whether he agrees with the assessment provided by PI. Reports for events determined by either the investigator or research monitor to be possibly or definitely related to participation and reports of events resulting in death will be promptly forwarded to the USAMRMC ORP HRPO by the study team.

If the investigator and/or the medical monitor believe the AE is serious, study related (possibly, probably or definitely), and unexpected, the SAE will be sent immediately to the DSMB. The determination of a probable or possible relationship to the hypothermia treatment will be discussed with the DSMB to determine what, if any, action should be taken with regard to continuation of the trial.

Following the determinations made by the DSMB, the PI will distribute all appropriate information to the clinical sites and their respective IRBs per local requirements. Finding of a significant number of study-related AEs and SAEs may lead to a change in consent forms or lead to decisions about modifying the protocol or discontinuing the trial.

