#### 7. **MANAGEMENT OF ADVERSE EXPERIENCES**

Adverse events will be graded according to the USDHHS Common Terminology Criteria for Adverse Events V4.0 (USDHHS, Table 2) and summarized according to body system. Primary focus for analysis will be on 6-month mortality rate, incidence of pneumonia, incidence of DVT/PE, incidence of bleeding and incidence of arrhythmia. For the purpose of safety monitoring, adverse events in the table below of Grade 3 or higher will be classified as "Important AEs" or selected AEs of interest.

Table 2. Selected AEs	Table 2. Selected AEs from USDHHS Common Terminology Criteria for Adverse Events V4.0 USDHHS									
Adverse Event	Grade 1	Grade 2	Grade 3	Grade 4	Grade 5					
Sinus Bradycardia	Asymptomatic, intervention not indicated	Symptomatic, medical intervention indicated	Severe, medically significant, medical intervention indicated	Life-threatening consequences; urgent intervention indicated	Death					
Supraventricular tachycardia	Asymptomatic, intervention not indicated	Non-urgent medical intervention indicated	Medical intervention indicated	Life-threatening consequences; hemodynamic compromise; urgent intervention indicated	Death					
Ventricular arrhythmia	Asymptomatic, intervention not indicated	Non-urgent medical intervention indicated	Medical intervention indicated	Life-threatening consequences; hemodynamic compromise; urgent intervention indicated	Death					
Thromboembolic event	Venous thrombosis (e.g., superficial thrombosis)	Venous thrombosis (e.g., uncomplicated deep vein thrombosis),	Thrombosis (e.g., uncomplicated pulmonary embolism [venous],	Life-threatening (e.g., pulmonary embolism, cerebrovascular event, arterial	Death					

			1	02/23/	2018                                    
		medical intervention indicated	nonembolic cardiac mural [arterial] thrombus), medical intervention indicated	insufficiency); hemodynamic or neurologic instability; urgent intervention indicated	
Pneumonia			Dyspnea and pneumonia symptoms (e.g., aspiration pneumonia); hospitalization indicated; unable to aliment orally	Life-threatening respiratory or hemodynamic compromise; intubation or urgent intervention indicated	Death

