#### **9.2.2 Secondary outcomes.** Secondary outcomes will include:

- adverse event rates (e.g., infection, pneumonia, hemorrhage, thrombosis)
- ICU LOS, hospital LOS
- incidence of cortical spreading depolarization

• levels of biomarkers (e.g., GFAP, UCH-L1)

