# 9.5 Data Analyses

The primary analysis population will be an Intention-to-Treat population, all randomized subjects, followed by an As-Treated analysis for sensitivity. As described below, for the primary outcome, 4-week DRS will be used to impute missing 6-month GOSE for the interim analyses. Demographic and baseline laboratory results will be summarized using descriptive statistics, including means, standard deviations, medians, ranges, histograms and box-plots. Fisher's exact test and Wilcoxon rank sum test will be used in the data analyses of categorical and continuous variables, respectively. Adverse events will be reported by type, frequency and severity.

9.5.1 Statistical Modeling. The National Acute Brain Injury Study: Hypothermia II (NABIS:H II) shows that there was a strong correlation between 4-week Disability Rating Scale (DRS) and 6month GOSE (Table 1). In particular, there were 2 false negatives out of 45 patients (4%) and 6 false positives out of 30 patients (20%). It shows that the short-term response is a good predictor for 6-month GOSE.

Table 3 summarizes the historical data (NABIS:H II study) comparing the 4-week DRS score and 6-month outcome; 80% (24/30) of good short-term DRS had a good long-term GOSE, while 4% (2/45) poor DRS had a good GOSE:

Table 3

	6-month GOSE		
4-week DRS Score	Poor	Good	Total
Poor (19 or larger)	43 (96%)	2 (4%)	45
Good (18 or less)	6 (20%)	24 (80%)	30

The statistical model used in this study explicitly models the relationship between 4-week DRS and 6-month GOSE score. Let pDc and pDt be the probabilities of good 4-week DRS scores in the control and treatment groups. Furthermore, define

 $p_{Gc0} = Pr(GOSE good | control, DRS poor)$ 

 $p_{Gc1} = Pr(GOSE good | control, DRS good)$ 

pGt0 = Pr(GOSE good | treatment, DRS poor)

pGt1 = Pr(GOSE good | treatment, DRS good)

These probabilities define the conditional probabilities of achieving a good GOSE score given the DRS score and treatment group.

Together, pDc, pDt, pGc0, pGc1, pGt0, and pGt1 define a joint distribution over DRS and GOSE scores. The key parameter of interest is the probability of a good GOSE score within each group, which can be derived from these parameters.

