#### 9.5.3 Interim Analysis on Safety.

The probability of selected adverse events of interest (defined in Section 7), and separately of deaths, will be monitored based on a beta-binomial model. Enrollment will be placed on hold pending DSMB review if the proportion of selected adverse events of interest in the treatment arm is too high in comparison to the control arm or if the proportion of deaths in the treatment arm is too high in comparison to the control arm. The selected adverse events of interest will also include patient deaths.

The DSMB will perform a more detailed review of the selected AEs of interest to determine if the study should continue. In particular, enrollment will be placed on hold if,  $Pr(p1 > p0 \mid data) > 0.98 \text{ OR } Pr(pdeath1 > pdeath0 \mid data) > 0.98$ ,

where p1 and p0 are the proportion of patients with selected AEs of interest in the hypothermia and control arms, respectively, and pdeath1 and pdeath0 are the proportion of patients that died. The prior distributions for p1, p0, pdeath1, and pdeath0 are independent, ran-informative Beta (1, 1). The 0.98 thresholds were selected to adjust partially account for the multiple interim analyses scheduled to occur. We will start to perform the interim analysis on safety for the first 10 patients in each arm randomized, and then other interim analyses will be carried out every 10 patients in both arms (20 patients). The operating characteristics for the stopping rules under various scenarios are summarized in Table 5, with results based on 10000 simulations.

Table 7. summarized the simulation results with interim analyses for safety every 20 patients randomized, assuming there will be 120 patients (60 per arm).

Table 7

Scenario	Selected AEs of	Death		
	Interest	Interest proportions		
	proportions		% trials with at least one	Mean number
	(Control, Treatment)	(Control, Treatment)	hold for safety evaluation	of pts
1	(0.25, 0.10)	(0.125), 0)	0.08%	120
2	(0.25, 0.15)	(0.125, 0.025)	0.4%	120
3	(0.25, 0.25)	(0.125, 0.125)	7.5%	115
4	(0.20, 0.30)	(0.10, 0.20)	39.7%	96
5	(0.20, 0.40)	(0.10, 0.30)	81.1%	66
6	(0.20, 0.50)	(0.10, 0.40)	97.4%	45
7	(0.20, 0.60)	(0.10, 0.50)	99.8%	33

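### Section 10.4 makes causation by the research part of the definition of an adverse event, which conflicts with the type-and-grade counts in Sections 7 and 9.5.3 and with Section 10.4's own later relatedness step

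*Combined protocol and SAP*

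**What the plan says.** Section 10.4 defines an AE as an undesirable, unintended "event occurring in human subjects as a result of (a) the interventions and interactions used in the research" or of the collection of private information. The serious category is built on it: "A Serious adverse event is an adverse event that led to death, or to serious deterioration in the health of the subject". No other section defines the term.

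Section 7 works differently. For safety monitoring, "adverse events in the table below of Grade 3 or higher will be classified as" important, or selected AEs of interest. The criteria are the Table 2 list and the grade; attribution is not mentioned. The analysis focus is 6-month mortality and "incidence of pneumonia, incidence of DVT/PE, incidence of bleeding and incidence of arrhythmia".

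Section 9.5.3 uses these events in the hold rule, "where p1 and p0 are the proportion of patients with selected AEs of interest in the hypothermia and control arms". It adds: "The selected adverse events of interest will also include patient deaths". No cause of death is asked for.

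Later in Section 10.4, sites report all fatal events and SAEs. The investigator and the research monitor then assess the relationship to the study, and the text refers to AEs that are study-related as a subgroup.

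Two further places use the term without defining it. Section 9.2.2 lists "adverse event rates (e.g., infection, pneumonia, hemorrhage, thrombosis") as a secondary outcome, and Section 9.5 says "Adverse events will be reported by type, frequency and severity".

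**The concern.** A Grade 3 pneumonia that the site puts down to the head injury or to ventilation is not an AE under 10.4, yet it is a Table 2 event of qualifying grade under Section 7. One site could leave it out and another record it, each following the protocol.

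The filter need not act equally in the two arms. Sections 2.2, 10.4 and 11.4 name pneumonia, thrombosis and arrhythmia among the risks of hypothermia or of the catheter, so such an event is easier to attribute to the research in a cooled patient than in a control. Blinding is specified only for the GOSE and DRS assessors (Sections 6.3.6 and 9.2.1). This is an inference about risk, not evidence of what sites do.

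At stake are the non-fatal part of the hold rule and the AE rates behind the safety objective. Both could partly reflect who attributed what, rather than what happened in each arm.

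**Working it through.** **Reading the sections together.** If every AE is caused by the research by definition, then assessing its relationship afterwards, or singling out study-related AEs, has no content. If all deaths are selected AEs (9.5.3), the 10.4 test is not being applied to deaths. So 10.4 fits neither its own later paragraphs nor 9.5.3. For non-fatal events, Section 7 points to counting by type and grade, but no section says that attribution is to be ignored.

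**Inputs from Section 9.5.3.** Looks after 20, 40, 60, 80 and 100 patients (10 to 50 per arm); independent Beta(1,1) priors; hold if Pr(p1>p0) > 0.98 or Pr(pdeath1>pdeath0) > 0.98. With x patients affected out of n in an arm, the posterior is Beta(1+x, 1+n−x). Deaths are simulated as a subset of selected AEs; treating them as independent of, or added to, the AEs does not reproduce Table 7 (50.1% or 53.9% in scenario 4, against 39.7% stated).

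**Reproducing Table 7** (100,000 simulated trials per cell; Monte Carlo error at most about 0.16 points; repeat runs differ by a few tenths of a point):

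| Scenario | 1 | 2 | 3 | 4 | 5 | 6 | 7 |
|---|---|---|---|---|---|---|---|
| Stated, % | 0.08 | 0.4 | 7.5 | 39.7 | 81.1 | 97.4 | 99.8 |
| Simulated, % | 0.11 | 0.57 | 7.8 | 40.2 | 80.5 | 97.2 | 99.8 |

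**Assumed loss.** Deaths are always counted. Each non-fatal event is recorded with probability f. A patient with k independently recorded events counts with probability 1−(1−f)^k. The documents give neither f nor k; k = 1 unless stated.

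*Equal true rates (scenario 3: AE 0.25, death 0.125 in both arms), chance of any hold:*
- full recording: 7.7%
- control arm only loses 10%, 25%, 50%: 8.7%, 10.9%, 17.1% (11.1% at half lost with k = 2)
- hypothermia arm only loses half: 4.5%
- both arms lose half: 6.8%

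*The plan's harm scenarios 4 / 5 / 6:*
- full recording: 40.3 / 80.8 / 97.2%
- both arms lose half: 38.9 / 79.8 / 96.9%, a fall of 1.4 / 1.0 / 0.3 points
- hypothermia arm only loses half: 33.3 / 76.5 / 96.2%
- control arm only loses half: 52.9 / 87.3 / 98.5%

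Equal loss matters little here because the non-fatal share (AE minus death) is the same in both arms. In scenario 5 it is 0.20−0.10 = 0.10 for control and 0.40−0.30 = 0.10 for hypothermia. The excess is all in deaths, which are kept.

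*Assumed case outside the plan (AE 0.20 v 0.40, death 0.10 in both arms):*
- full recording: 63.6%
- both arms lose half: 29.2% (46.3% with k = 2)
- hypothermia arm only loses half: 14.2% (35.3% with k = 2)

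**AE rate as an outcome.** Recorded rate = death + (AE − death) × recorded share. With equal true rates and half of control non-fatal events lost, control shows 0.125 + 0.125 × 0.5 = 0.1875 against 0.25, a false difference of 6.25 points. With k = 2 it is 0.125 + 0.125 × 0.75 = 0.219, a difference of 3.1 points.

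**The case against.** The operating text leans towards recording first and attributing later. Section 7 classifies by type and grade, Section 6.3.7 documents abnormal laboratory values by grade, the Section 6.1 schedule has AE assessments for all patients from entry to 6 months, and the Section 10.1 forms cover disease- and injury-related events. Controls also receive the study catheter, so some of their events meet 10.4 as written. That sites would filter before recording is conjecture, and no stated figure is wrong. All of this stands. It limits the consequence but leaves the only definition at odds with the counts.

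Four stronger readings are tempting, and the documents do not support them:

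- *The plan specifies all-cause counts that 10.4 breaks.* No section says so. For non-fatal events it is the plain reading of Sections 7 and 9.5.3, not a stated rule.
- *Sections 9.2.2 and 9.5 also contradict 10.4.* They only use the term and can inherit its definition. Their AE rates would then carry the attribution filter, which is a consequence rather than a second contradiction.
- *Agreement with Table 7 shows that it assumes complete recording.* Its AE proportions are inputs and could be recorded rates under any definition. The match confirms the algorithm and that deaths lie within the AE count, nothing more.
- *Equal under-recording cripples the AE criterion in the plan's harm scenarios.* That needs deaths to be lost from the AE count, contrary to 9.5.3. With deaths kept and half of non-fatal events lost in both arms, the AE criterion alone in scenario 5 goes from about 63.6% to 68.2%.

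**Conclusion.** The definition in 10.4 is wrong as written for the use made of it, and it should be reconciled with Sections 7 and 9.5.3 and with 10.4's own relatedness step. The conflict is firm because it rests on the text. Its effect is conditional on literal application of 10.4, on attribution by staff who know the arm, and on loss fractions that the documents do not give.

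Under those assumptions, a one-sided loss can raise the null hold rate from about 7.7% to between 9% and 17%, or lower it to 4.5%, depending on which arm loses events. Equal loss barely touches the plan's harm scenarios. The real exposure is harm confined to non-fatal events, where the death criterion gives no backup, and the plan simulates no such case. Deaths are protected and a hold prompts DSMB review rather than a stop. The consequence is therefore a misdirected or missed review of non-fatal events, and AE rates that are hard to interpret.

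**What to change.** - In Sections 7, 9.5.3 and 9.2.2, state that every Table 2 event of Grade 3 or higher after randomisation is recorded and counted in both arms, regardless of attribution.
- In Section 10.4, either take causation out of the AE definition or state that the definition does not limit these counts.
- Keep relatedness as a separate recorded field.

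The cost is protocol and case-report-form wording, plus more AE entries; the documents give no basis for saying how many. If the general definition is widened, SAEs widen with it, because they are defined from AEs. That brings more 24-hour entries, medical-monitor notifications and forwarding to the DSMB, unless expedited reporting is tied to the relatedness field. The narrower option, leaving the definition and stating that it does not limit the counts, avoids most of that.

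Neither option removes bias in detecting or grading events by unblinded staff.

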# 11. HUMAN SUBJECTS

# 11.1 Institutional Review Board (IRB) Review and Informed Consent

This protocol and the informed consent document and any subsequent modifications will be reviewed and approved by the IRB responsible for oversight of the trial at each of the participating centers. A signed consent form will be obtained for every subject when feasible. Since subjects in this trial cannot consent for themselves, a LAR, or person with power of attorney, must sign the consent form. The consent form will describe the purpose of the study, the procedures to be followed, and the risks and benefits of participation. A copy of the consent form will be given to the LAR, and this fact will be documented in the subject's record. A proposed Informed Consent template is attached as **Appendix I.** If a subject is enrolled in the study and subsequently dies prior to obtaining consent, when feasible, the investigator will inform the subject's LAR or family members about the subject's participation personally at the earliest feasible opportunity. The study team will work within existing hospital practices to locate patients' next of kin. The study will maintain copies of medical record documentation indicating efforts made to identify the subject and their next of kin. If the hospital team (e.g.,

social work) identifies next of kin, after the hospital team has contacted the next of kin and informed them of the subject's death we will attempt to talk with family about the subject's participation in the study for up to 5 days after death. In cases where it is not feasible to provide information to the subject (e.g.,death, mentally incompetent) or the LAR/family (e.g., identitiy never determined) each site is requested to obtain a HIPAA Privacy Rule waiver to allow study use and retention of the data.

#### 11.2 Subject Confidentiality

All CT scans, evaluation forms, reports, and other records required by this trial that leave the site will be identified only by the Uniform Identification Number (UID) to maintain subject confidentiality. All on-site records will be kept in a locked file cabinet. All computer entry and networking programs will be done using SIDs only. Clinical information will not be released without written permission of the subject, except as necessary for monitoring by IRB, or the Office of Human Research Protection (OHRP).

#### 11.3 Study Modification/Discontinuation

The study may be modified or discontinued at any time by the sponsor, the OHRP, or other government agencies as part of their duties to ensure that research subjects are protected. An individual IRB may discontinue the study at the clinical site it oversees, but the action is limited to that individual site.

